### Protocol Summary

Title of Study:	Two-Arm, Single Blind, Randomized Post-Market Study on the use of HEALICOIL™ REGENESORB Suture Anchor in the repair of tears of the rotator cuff
Study Type:	Postmarket
Primary Investigator:	[name]
Primary Endpoint:	85% high quality ossification at anchor site for HEALICOIL REGENESORB and 49.9% high quality ossification for TWINFIX Ultra HA at 24M
Secondary Endpoints:	Repair success rate (Defined as subjects without a re-tear or re-intervention) between groups, Pain/Function (VAS, WORC, PENN, SANE, EQ-5D, ROM), Patient Satisfaction, Difference in complication rates between groups
Design:	Prospective, randomized, two-arm, single-blind study
Length of Study:	24M follow-up
Sample Size:	68 subjects

### Schedule of Events

	BL	Proc	6WK	6M	12M	24M
Informed Consent	✓	-	-	-	-	-
Inclusion/Exclusion	✓	-	-	-	-	-
Demographics/Medical History	✓	-	-	-	-	-
Surgical Details	-	✓	-	-	-	-
Physical Exam-ROM	✓	-	✓	✓ 1	-	✓
Visual Analogue Scale (VAS)	✓	-	✓	✓	✓	✓
PENN	✓	-	✓	✓	✓	✓
WORC	✓	-	✓	✓	✓	✓
SANE	✓	-	✓	✓	✓	✓
EQ-5D	✓	-	✓	✓	✓	✓
Ultrasound	-	-	-	✓ 2	-	-
MRI	-	-	✓	-	-	-
CT Scan	-	-	-	-	-	✓
Patient Satisfaction	-	-	✓	✓	✓	✓

Adverse Event Assessment	-	√	√	√	√	√
End of Study/Exit	*	*	*	*	*	*

Physical Exam at 6M will occur at the same visit as the 6+ month ultrasound.

Ultrasound will be done at  $\geq$  6 months post-procedure.

\* End of Study will be noted on study spreadsheet at any point throughout the trial.

## 1. Background and Information

Rotator cuff disease is the most common cause of shoulder pain, and as the aging population is increasingly active and less willing to accept functional limitations, the incidence of this disease is expected to grow (Gomoll 2004, Coghlan 2008). While a large proportion of patients presenting with rotator cuff disease are asymptomatic, research has shown that over 50% of individuals with asymptomatic rotator cuff tears will develop pain over an average of 2.8 years (Yamaguchi 2001). Although not life-threatening, a rotator cuff tear can cause significant pain, weakness, and limitation of motion (Crusher 2000). Once a tear occurs, it is unlikely to heal without treatment, and left untreated, large tears may result in chronically retracted muscle-tendon units that undergo fatty degeneration resulting in weakness, a potentially irreversible process (Fukuda 2003, Gomoll 2004). Thus, once a tendon ruptures, the primary method of repair is surgical intervention, focusing on the re-establishment of the interface between the tendon and bone. Tendons are typically very slow to heal, and as such, prolonged immobilization and lengthy rehabilitation are required. An effective treatment that shortens the duration of symptoms and disability has the potential to be of significant value in terms of reduced morbidity and costs to both the individual and the community (Coghlan 2008).

Standard treatment of full thickness rotator cuff repairs involves tissue reattachment. This can be accomplished by various techniques, with the gold standard being suture anchors plus suture fixation. First generation suture anchors were made of metal and were initially well received- reporting pull out strengths rivaling that of other suturing techniques, however, reports of loosening, migration, chondral injury, revision surgery, and magnetic resonance imaging interference has led device makers to explore other materials. The desire for a high strength anchor without the issues that metallic anchors presented has led to the creation of plastic and bioabsorbable suture anchors. PEEK, for instance, is not biodegradable but is radiolucent, allowing good post- operative imaging. As a plastic, it also affords solid fixation strength yet remains soft enough for a revision surgery drill through. These characteristics have made PEEK anchors popular, emerging in numerous designs and indications.

The advantage of bioabsorbable material over its plastic (such as PEEK) counterpart is it allows for the restoration of natural anatomy as it resorbs, which in turn eases revisions as there is no need to drill through an existing anchor. Bioabsorbables include a wide array of materials composed of natural, synthetic, or biosynthetic polymers. There are more than forty types of polymers that have been developed for use in surgery. More widely known types of these polymers are polyglycolic acid (PGA) and polylactic acid (PLA), along with their many variations. The poly-L-lactic acid (PLLA) variation was once considered the gold standard of bioabsorbable materials, however; clinical information and animal studies have since demonstrated that the degradation properties of PLLA are slow, taking as many as five to seven years to degrade with no evidence of replacement by bone. Instead, replacement by fibrous or fatty-fibrous tissue has been seen. Because of these limitations, composite materials consisting of polymer and ceramic blends are emerging as materials for suture anchors. Bioactive ceramics are known to be osteoconductive on their own and have been clinically proven for use as bone graft substitutes. Utilization of the appropriate polymer variation is thought to increase the likelihood of maintaining mechanical strength through the healing period while subsequently assuring timely degradation to avoid the complications seen in the long term absorbable implants.

Despite the developments in suture anchor technology, concern remains about how well the rotator cuff heals back to the insertion site after repair. Clinical studies have shown the rate of radiographic failures at the repair site to occur anywhere from 11% to 95% of patients (Fealy 2006, Galatz 2004, Harryman 1991, Lafosse 2007, Gerber 2000, Boileau 2005). Patients who fail to heal or who re-tear may still experience pain relief, although they have inferior functional results compared with patients

whose repairs have healed (Galatz 2004, Harryman 1991). In an effort to minimize failures, stronger sutures and new repair techniques have been developed in an attempt to improve biomechanical strength (Lafosse 2007). In spite of these new techniques, approximately 20% of patients fail to heal or experienced a re-tear (Slabaugh, 2010). Smith & Nephew has designed a bioabsorbable suture anchor that, due to its design, maybe impact healing at the tendon- bone interface.

In a pre-clinical ovine study, HEALICOIL™ REGENESORB demonstrated osteointegration beginning at 12 weeks post-implantation. This study will seek to replicate these findings in humans. Magnetic resonance images (MRIs) at an early time point will be used to show the screws in contrast to bone and soft tissues, enabling the radiologist to provide screw measurement and determine percent bony ingrowth. The CT at 24 months should allow for a more drastic transition to the cortical-like bone making the bone to remnant anchor material more apparent.

## **2. Study Design**

This is a prospective, randomized, two-arm study to assess the outcomes of the HEALICOIL REGENESORB suture anchor compared to the TWINFIX™ Ultra HA suture anchor when used in rotator cuff repair. A total of 68 subjects will be enrolled at the research site.

## **3. Study Objectives**

The purpose of this study is to compare the clinical and radiographical outcomes of HEALICOIL REGENESORB suture anchor (open design) vs. TWINFIX Ultra HA suture anchor (closed design) in patients requiring rotator cuff repair.

### **3.1. Study Endpoints**

#### **3.1.1. Primary Endpoint**

85% high quality ossification at anchor site for HEALICOIL REGENESORB and 49.9% high quality ossification for TWINFIX Ultra HA at 24M

#### **3.1.2. Secondary Endpoints**

- Repair success rate (Defined as subjects without a re-tear or re-intervention) between groups as determined by ultrasound
- Difference in pain/function from baseline on the following:
  - Visual analog scale (VAS) pain score,
  - Western Ontario for Rotator Cuffs (WORC)
  - PENN Shoulder Score (PENN)
  - Single Assessment Numeric Evaluation (SANE)
  - EQ-5D
  - Range of motion (ROM).
- Patient Satisfaction

#### **3.1.3. Safety Endpoints:**

- Adverse Events
- Difference in complication rates between groups

## **4. Study Material**

The Smith & Nephew HEALICOIL REGENESORB Preloaded Suture Anchors consist of an absorbable suture anchor with an attached non-absorbable suture assembled to an insertion device. The suture anchors are intended to provide secure reattachment of soft tissue to bone.

## **5. Control Device**

The control device selected for this study is the TWINFIX™ Ultra HA suture anchor, which is approved for use in rotator cuff repair.

## **6. Study Population**

This clinical study of the HEALICOIL™ REGENESORB suture anchor can fulfill its objectives only if appropriate subjects are enrolled. All relevant medical and non-medical conditions should be taken into consideration when deciding whether a particular subject is suitable. The subject recruitment period will continue until the study enrollment limit of 68 subjects is reached.

### **6.1. Subject Recruitment and Screening**

#### **6.1.1. Screening**

Patients who present with the need for rotator cuff repair will be screened for inclusion into the study. Following discussion of the study between the patient and the treating physician, the patient will be given the opportunity to move forward with the informed consent process.

#### **6.1.2. Enrollment**

The subject will be considered enrolled once voluntary informed consent has been given, and the form has been signed and dated by all required parties.

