#### **6.1.3. Randomization**

Subjects will be randomized to a treatment arm using a 1:1 ratio. Once study eligibility has been confirmed, the study coordinator or designee will randomize the subject to a treatment arm. The treatment for each subject will be assigned through the study database.

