## **6.2. Subject Inclusion Criteria**

Subjects must meet all of the following characteristics for inclusion in the study.

- Male or female, aged 35 to 75 years at the time of surgery.
- Willing and able to give voluntary informed consent to participate in this investigation.
- Full thickness tear of the rotator cuff
- Tear requires repair within one year of initial diagnosis.
- Tear must be anatomically repairable (must be able to get tendon back to the medial position on the footprint and at least back to the tuberosity).

- Willing and able, in the opinion of the Investigator, to cooperate with study procedures, and willing to return to study site for all required post-operative study visits.

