### 6.3. Subject Exclusion Criteria

Subjects with any of the following characteristics must be excluded from participation in the study.

- Evidence of acute trauma including fracture or dislocation of the shoulder joint.
- Chronic retraction.
- Evidence of active infection, osteomyelitis, sepsis or distant infection, which could spread to the index joint.
- Subject has had previous rotator cuff, arthroplasty or fracture procedures on the operative shoulder.
- Subject has had acromioplasty or diagnostic arthroscopy on the operative shoulder within one (1) year prior to scheduled surgery date.
- Evidence of osteomalacia or other metabolic bone disorder(s), which may impair bone or soft tissue function.
- Evidence of other significant shoulder pathology including (Type II-IV lesion, Bankart lesion, Hill Sachs lesion).
- Patient has grade 4 changes to articular cartilage in operative shoulder
- Inflammatory arthropathies.
- Significant muscle paralysis of the shoulder girdle.
- Painful pathologies of the cervical spine.
- Comminuted bone surface, which would compromise secure anchor fixation.
- Non-surgical rotator cuff associated treatment, such as corticosteroid injection, within one (1) month prior to scheduled surgery date.
- Participating in another investigational trial or ongoing study that would interfere with the assessment of the primary and secondary outcomes.
- Female patient who is pregnant, nursing, or of childbearing potential while not practicing effective contraceptive methods.
- Major psychiatric illness, developmental handicap or inability to read and understand the English language.
- Major medical illness that would preclude undergoing surgery.
- Known to be involved in any active injury litigation claims relating to the study shoulder.
- Unwilling or unable to be assessed according to study protocol for two years following surgery.
- Patient requires a concomitant SLAP repair procedure in operative shoulder.
- Surgeon plans to use a Platelet Rich Plasma product or another therapy intended to augment healing of the rotator cuff in the study procedure.
- Protocol specified surgical technique cannot be followed for this subject.
- Rotator cuff repair will be done via open (as opposed to arthroscopic) procedure.

- Any other reason (in the judgment of the investigator).

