#### **6.4. Withdrawal of Subjects from Study**

All reasonable efforts should be made to retain the subjects for the duration of this study. Once a subject has been withdrawn from the study (pre-maturely or at completion of the study), the study termination form should be completed.

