##### **6.4.1. Voluntary Withdrawal by Subject**

Study participation is voluntary and subjects may withdraw at any point during the study. If a subject withdraws from the study, the investigator will make all reasonable efforts to determine the reason for the subject's withdrawal and will document the reason on the applicable form. After a subject withdraws from the study, no effort will be made to replace or follow the subject.

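### Do the 68 subjects count consents or randomised subjects, and is a randomised subject later found ineligible left without a rule?

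*Combined protocol and SAP*

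**What the plan says.** Section 6.1.2 (Enrollment): "The subject will be considered enrolled once voluntary informed consent has been given". Section 6 (Study Population): "The subject recruitment period will continue until the study enrollment limit of 68 subjects is reached". Section 2 likewise gives 68 as the number to be enrolled.

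Section 6.1.3 (Randomization): "Once study eligibility has been confirmed, the study coordinator or designee will randomize the subject to a treatment arm". It names no visit. Both schedules (Protocol Summary, and Table 1 in section 8.2.6) tick inclusion/exclusion at baseline only and have no randomisation row.

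Some eligibility criteria concern what a surgeon may see at operation. Section 6.2 requires a tear that can be repaired back to the footprint. Section 6.3 excludes "Comminuted bone surface, which would compromise secure anchor fixation" and "Protocol specified surgical technique cannot be followed for this subject".

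On retention, section 6.4 states "All reasonable efforts should be made to retain the subjects for the duration of this study". Section 6.4.1, under voluntary withdrawal, states "After a subject withdraws from the study, no effort will be made to replace or follow the subject". Section 6.4.2 gives a non-exhaustive list of reasons for withdrawal by the investigator, and ineligibility is not among them. Section 6.4.4 has completion status and the reason for withdrawal recorded. Section 8.2.5 provides a CT for every enrolled patient.

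Section 14 needs 27 per arm at 24 months (0.499 v 0.850, two-sided 0.05, 80% power), expects 20% drop-out counted from baseline, and targets 68. It defines no analysis population.

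**The concern.** Three details look loose when these sections are read together.

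- **The count.** If 68 is a number of consents and the 20% covers only losses after randomisation, every subject who consents and then fails eligibility takes a place that the power calculation had assigned to a randomised subject. The target has almost no slack.
- **The timing.** If assignment is drawn before surgery and a criterion is settled only at surgery, a randomised subject may turn out to be ineligible. Section 6.1.3.1 blinds subjects and the MRI and CT radiologists, not the surgeon, so an exclusion at that stage could depend on the arm.
- **The handling.** Section 14 does not say whether such a subject stays in the comparison, and the primary endpoint is scored at the anchor site, so a subject without a study anchor has nothing to score.

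At stake would be some power and, in principle, the comparability of the arms. With 27 per arm, one excluded subject is 1/27 = 3.7% of an arm.

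**Working it through.** **Inputs.** Control rate 0.499, test rate 0.850, two-sided 0.05, 27 per arm, 20% drop-out and 68 in total, all from section 14. The documents give no share of subjects found ineligible after consent, so the counts *k* below are assumptions.

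**1. The plan's own figures.** Pooled-variance two-proportion formula, with p̄ = (0.499 + 0.850)/2 = 0.6745 and difference 0.351:

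- √(2 × 0.6745 × 0.3255) = 0.6626; √(0.499 × 0.501 + 0.850 × 0.150) = 0.6144.
- n = (1.960 × 0.6626 + 0.8416 × 0.6144)² / 0.351² = 26.8, rounded up to 27 per arm.
- Power at 27 per arm: Φ[(0.351 × √27 − 1.960 × 0.6626) / 0.6144] = 80.4%. Exact power of the uncorrected chi-square test by binomial enumeration: 82.1%.
- Target: 2 × 27 / 0.8 = 67.5, rounded up to 68.

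The plan's figures reproduce.

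**2. Ineligibility inside the 20% (drop-out counted from baseline).** 68 × 0.8 = 54.4, against 54 needed. Up to 68 − 54 = 14 subjects (20.6%) may be lost for any reason. With *k* found ineligible, the room for drop-out among the rest is (14 − k)/(68 − k): k = 2 gives 12/66 = 18.2%, and k = 4 gives 10/64 = 15.6%. Nothing is lost against the plan.

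**3. Ineligibility on top of the 20%.** Evaluable per arm = (68 − k) × 0.8 / 2.

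| k (assumed) | Per arm | Formula power |
|---|---|---|
| 1 | 26.8 | 80.1% |
| 2 | 26.4 | 79.4% |
| 3 | 26.0 | 78.8% |
| 5 | 25.2 | 77.5% |

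Exact power is 81.1% at 26 per arm and 79.2% at 25, so it stays above 80% with three such subjects and falls just below with five to six.

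**4. The control rate.** Section 14 predicts that the control arm will fall short of 49.9%. At 26.4 per arm and an assumed control rate of 49% or 48%, formula power is 81.3% or 83.3%. A fall of one percentage point more than offsets the loss of two subjects.

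**5. Which reading the text supports.** Sections 2, 6 and 6.1.2 together make the 68 a count of consents. Both schedules and section 8.2.1 place consent at baseline, and the schedules place eligibility there too. A loss counted from baseline therefore starts at the same point as the 68, which is the reading in step 2. In addition, section 6.1.1 has patients screened before consent is offered, which limits how many would be found ineligible afterwards.

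**6. Timing and handling.** Section 6.1.3 orders the steps: eligibility, then assignment. No section says that the criteria on repairability, bone surface or technique are judged during the operation; that is an inference from their subject matter. Several neighbouring exclusions in section 6.3 are worded as plans made before surgery, which fits the baseline tick. For a subject found ineligible later, sections 6.4 and 8.2.5 point towards retention and a CT. The sentence against replacing or following subjects sits under voluntary withdrawal, and section 6.4.2 permits withdrawal without requiring it.

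**The case for a change.** The strongest case for a change concerns validity more than power. The surgeon knows the assignment at some point, section 6.3 ends with a discretionary exclusion, the list in section 6.4.2 is open-ended, and section 14 names no analysis set. Nothing expressly prevents an exclusion at surgery that depends on the arm, and a few sentences would close the door. If larger losses are assumed on top of the 20%, power also falls further: a 5% loss leaves 68 × 0.95 × 0.8 / 2 = 25.84 per arm and 78.5%, and a 10% loss leaves 24.48 and 76.2%.

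Part of this stands. Section 14 is silent on which randomised subjects enter the 24-month comparison, and section 6.1.3 gives no time point. But the silence covers all losses after randomisation and is not special to ineligibility. The arm-dependent exclusion needs two suppositions that the documents do not make: that assignment is known before the last eligibility judgement, and that subjects excluded then leave the analysis. The larger power losses need both an assumed rate and the less natural reading of the 20%.

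**Conclusion.** The concern does not call for a change. The count is answered by the document: 68 means consented subjects, and a subject found ineligible after consent uses one of the 68 places. On the natural reading of the 20%, the expected yield is 54.4 against 54 and the planned power of about 80% is intact. On the other reading, one to three such subjects cost at most 80.4 − 78.8 = 1.6 percentage points of formula power, and exact power stays at 81.1% or more.

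What remains is missing detail on the time of assignment and on the analysis set. No stated rule is wrong, and no result is shown to change. An analyst would ordinarily compare randomised subjects who have a 24-month CT in their assigned arms and list those without one by arm, using the reasons that section 6.4.4 already has recorded.

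This conclusion assumes that few subjects are found ineligible after consent, which the screening step supports but the documents do not quantify. It also assumes that later ineligibility is not treated as a ground for ending follow-up, which no section says it is.

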#### **6.1.3. Randomization**

Subjects will be randomized to a treatment arm using a 1:1 ratio. Once study eligibility has been confirmed, the study coordinator or designee will randomize the subject to a treatment arm. The treatment for each subject will be assigned through the study database.

#### **6.1.3.1. Blinding**

Study subjects and radiologists performing MRI and CT analysis will be blinded to the treatment assignment for the duration of the study to reduce the risk of bias.

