### **8.2.2. Visit 2- Procedure**

The following information will be collected at this visit:

- Surgical Information
- Device Details: Be sure to keep stickers from the device packaging and record device details in the patient medical record and the Operative source documentation form.
- Adverse Events: Record any adverse events experienced by the patient

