#### 8.2.5. Radiological Procedures

All enrolled patients will receive one CT scan over the course of their study participation. All CT Scans will be conducted utilizing the CT Protocol. Data will be captured on the CT Evaluation Form.

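### The blinding rule omits ultrasound, so the plan permits the re-tear call behind the repair-success endpoint to be made with knowledge of the arm

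*Combined protocol and SAP*

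**What the plan says.** The Protocol Summary labels the trial single-blind. Section 6.1.3.1 is the only operative blinding rule, and it lists who is covered: "Study subjects and radiologists performing MRI and CT analysis will be blinded to the treatment assignment for the duration of the study". The purpose it gives is to limit bias.

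Section 3.1.2 lists first among the secondary endpoints: "Repair success rate (Defined as subjects without a re-tear or re-intervention) between groups as determined by ultrasound". Both versions of the Schedule of Events, and section 8.2.3, provide for one ultrasound at six months or later. None of them says who acquires it, who reads it, or whether either person is masked.

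Three other places touch the subject without settling it:

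- Section 8.2.5 describes arrangements for one modality only: "All CT Scans will be conducted utilizing the CT Protocol. Data will be captured on the CT Evaluation Form".
- Section 8.2.2 asks the site to "record device details in the patient medical record and the Operative source documentation form".
- A footnote to the first Schedule of Events says: "Physical Exam at 6M will occur at the same visit as the 6+ month ultrasound".

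**The concern.** Whether a repaired tendon is intact or torn again on ultrasound is a reader's judgement, and a reader who knows which anchor was used may lean one way in doubtful cases. The protocol accepts this reasoning for MRI and CT. Its list leaves out the one modality that decides repair success.

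At stake is the credibility of a between-group comparison on a clinically important secondary endpoint. Section 1 itself reports worse function in patients whose repair fails to heal or re-tears. If the call was made unmasked and no images were kept, it could not be re-read under masking later.

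**Working it through.** **Who is covered.** Set the modalities beside the rule.

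| Modality | Timing | Role stated in the plan | Reader masked by 6.1.3.1? |
|---|---|---|---|
| MRI | 6 weeks | Screw measurement and bony ingrowth (section 1) | Yes |
| CT | 24 months | Imaging scheduled at the primary endpoint's time point | Yes |
| Ultrasound | 6 months or later | Decides repair success (3.1.2) | Not mentioned |

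No other section extends masking to the ultrasound reader or to site staff. At least the coordinator or designee who randomizes (6.1.3) knows the arm.

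**The plan's own figure.** Section 14 gives 27 per group for 0.499 versus 0.850, two-sided 5%, 80% power. The mean proportion is 0.6745.

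- n = [1.96 × √(2 × 0.6745 × 0.3255) + 0.8416 × √(0.499 × 0.501 + 0.85 × 0.15)]² / 0.351²
- n = (1.299 + 0.517)² / 0.1232 = 26.8, so 27 per group. Power at 27 is 80.4%.
- Dropout: 54 / 0.80 = 67.5, so 68 in total, or 34 per arm.

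The figure reproduces. It rests on the 24-month ossification endpoint, so the ultrasound question does not touch it. The plan gives no test, power or sample size for repair success.

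**Illustration of possible size.** Inputs:

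- Base re-tear rate b = 0.20, from section 1: "approximately 20% of patients fail to heal or experienced a re-tear".
- m = share of re-tears called intact in one arm, none in the other. Assumed 0.10 to 0.50; the document gives no basis for it.
- n = 34 per arm (all randomized) or 27 (the 24-month target). The ultrasound comes earlier than 24 months, so these serve as brackets.

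False difference = b × m:

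- m = 0.10: 0.20 × 0.10 = 2 points
- m = 0.25: 0.20 × 0.25 = 5 points
- m = 0.50: 0.20 × 0.50 = 10 points

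Changed calls run from 0.02 × 27 = 0.5 to 0.10 × 34 = 3.4 subjects in the affected arm.

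The 95% half-width uses the rates that would then be observed, which differ between arms: 1.96 × √([p₁(1 − p₁) + p₂(1 − p₂)] / n).

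- 20% versus 18%, n = 27: 1.96 × √(0.3076 / 27) = 20.9 points
- 20% versus 18%, n = 34: 1.96 × √(0.3076 / 34) = 18.6 points
- 20% versus 10%, n = 27: 1.96 × √(0.25 / 27) = 18.9 points
- 20% versus 10%, n = 34: 1.96 × √(0.25 / 34) = 16.8 points

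The false difference is thus between 2 / 20.9 = 10% and 10 / 16.8 = 60% of the half-width.

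**Sensitivity to the base rate.** Section 1 also reports radiographic failure in "anywhere from 11% to 95% of patients". At the low end, b = 0.11, the false difference is 1.1 to 5.5 points. The half-width runs from 1.96 × √(0.1871 / 27) = 16.3 points (m = 0.10) down to 1.96 × √(0.1499 / 34) = 13.0 points (m = 0.50). Because the shift is proportional to b, a higher base rate gives a larger shift, so these figures are not an upper bound. With so few events the normal approximation is rough.

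**The case against.** The strongest reply is that this is silence and not contradiction. The trial is declared single-blind, and masking the MRI and CT radiologists already goes beyond masking subjects. If those radiologists also read the ultrasound, they are masked for the whole study and there is no gap in practice. That is fair, and it limits the claim to what the plan permits. It does not remove the point, because nothing assigns the ultrasound to them.

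A reader might go further and infer that site staff read the scan unmasked. The document does not support that:

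- Sharing a visit with the physical exam does not mean that the same person does both.
- Device details in the medical record are open to anyone with access to it, whatever modality they read.
- Section 8.2.5 names no form for MRI either, yet MRI readers are masked, so a missing form says nothing about masking.

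The numerical range is also open to criticism. The miscall shares are assumed, all errors are placed in one arm, and the quoted base rates do not include re-intervention, which is part of the endpoint. This stands. The range shows scale and is not evidence that bias exists or how large it would be.

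Finally, the plan specifies no test or power for repair success, so no powered conclusion depends on it. That lowers the weight of the point, but the endpoint is still a stated comparison between groups.

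**Conclusion.** The point holds as a gap in the rule: an explicit list of masked parties leaves out whoever makes the ultrasound call that decides repair success. The omission is certain on the text. Whether any call would be made unmasked, and whether bias would follow, is unknown.

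Under the stated assumptions at a 20% base rate, the effect runs from negligible (2 points) to large enough to move the estimate noticeably (10 points), though still inside the confidence interval half-width. It should not be read as a threat to the trial's main result: the CT readers are masked, and 27 per group and 68 in total stand. This is a low-cost improvement to a secondary endpoint, worth making.

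**What to change.** In section 6.1.3.1, extend the rule for image readers to cover MRI, CT and ultrasound analysis. Store the ultrasound images under the subject ID (section 6.1.4) without arm labels. Base the re-tear call used for the endpoint on a read by someone masked to the arm. The radiologists already masked could do this if they can read ultrasound, which the document does not say. Where feasible, keep the person acquiring the scan unaware of the arm too.

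The cost is a wording change, image storage and at most 68 reads, one per subject. It needs no extra subjects, visits or scans.

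The change reduces the risk without removing it. An unmasked operator still chooses the images. Section 3 describes one anchor as open and the other as closed in design, so a reader might recognise the device, as could already happen on MRI and CT. The re-intervention part of the endpoint is not masked by this change.
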